### 3.7.2. Perspectives

The perspective is the viewpoint from which costs and monetary benefits are considered.

The payer's (health insurance) perspective estimates costs from the "third-party payer" point of view. This perspective considers only the part of health care expenses (both inpatient and outpatient care) that are charged to or reimbursed by the health insurance.

This economic evaluation, based on direct medical costs, will be performed according to the payer's perspective.

All resource consumption data analysis will be specified in a separate Health Economics Analysis Plan.

## 4. Ethical consideration

### 4.1. Informed Consent Form

Patient's participation in the study is voluntary. The patient's consent may be withdrawn at any time, without giving reasons and without prejudice to further medical care.

The study participants will be informed in writing and orally before the start of the study about the nature and scope of the planned investigation, in particular about the possible benefits for their health and possible risks, and their consent will be documented by signing the consent form.

Informed Consent Form (ICF) consisting of two documents (Informed consent with participation in the Study and Patient's personal data protection Inform consent) will be obtained from each patient prior to study initiation. Two original documents will be signed by the patient. One original Informed Consent Form (ICF) will be filed with the patient's documentation in the clinical center and the second original Informed Consent form will be given to the patient.

CONFIDENTIAL

Confidential	MyRisk	Date: 05 February 2024
	Protocol	
	PROTOCOL NUMBER: IBA1160	Version: 5.1

IBA will prepare the Master Informed Consent Form in English according to the European requirements. The Master Form will be then distributed to all the coordinators of the respective countries (local CROs). Each coordinator (local CRO) will have to review the Master Informed Consent Form and add in track changes the sentences or expressions possibly required by the local Health Authorities and local legislative. The document with tracked changes (including deletions if applicable) will have to be sent back to IBA for the translation in the local language.

## 4.2. Regulatory Requirements

The study will be conducted in accordance with the Helsinki Declaration in its current version and all local laws or regulations.

Submission to Ethics Committee and local Health Authorities and relevant approvals are required and will be performed at the local national level by the coordinator of the respective country (local CRO).

## 4.3. Legislative Requirements

Local legislative requirements of the countries in which the study takes place will be applied.

Legislative requirements regarding personal data protection are described in the following section 9. Confidentiality. The study protocol and the study results will be posted in EUDRACT and ClinicalTrials.gov in accordance with regulatory requirements and timelines.

Notification to Data protection Authorities in individual countries will be applied according to the local regulatory and legislative requirements.

CONFIDENTIAL

Confidential	MyRisk	Date: 05 February 2024
	Protocol	
	PROTOCOL NUMBER: IBA1160	Version: 5.1

## 5. Monitoring

The purposes of trial monitoring are to verify:

- 1) The rights and well-being of human subjects are protected
- 2) The trial data are accurate, complete, and corresponding with the source documents (medical records)
- 3) The study is conducted in compliance with the currently approved protocol and its amendments, GCP requirements, and with the relevant regulatory requirements.

ICH E6 (R2) provides for flexibility in how trials are monitored, advising sponsors to consider “the objective, purpose, design, complexity, blinding, size, and endpoints of a trial” in determining the extent and nature of monitoring for a given trial.

Quality risk-based monitoring approaches can be highly effective in phase IV and are supported by regulatory guidance.

Generally applying the integrated approach of Quality Risk-Based Monitoring in conjunction with procedures, such as investigators' training, and written guidance can assure appropriate conduct of a post-approval study in accordance with ICH GCP requirements.

This clinical study is post-registration clinical study phase IV where the medicinal product is used in accordance with SPC. The only intervention is randomization, so this kind of monitoring will be implemented in this study.

Quality Risk-Based Monitoring enables focused attention of risk while promoting efficient utilization of time, resources, and budget. Risk management including the used procedure within this study is described in chapter 5 (Risk management and Risk assessment).

Due to the extent, budget, and nature of the study the remote monitoring (remote evaluation of collected data, performed in a timely manner supported by appropriately qualified and trained persons (data managers, biostatisticians) will be primarily applied. The processes of data control and data review are described in the following chapters of this document. The effectiveness and efficiency of this strategy will be regularly monitored in compliance with the Risk management plan.

In the event the controls will disclose the system error at the site, the following process will depend on the scope and difficulty to eliminate the discrepancy. Correction by the distant way (teleconference with IBA HelpDesk assistant or data manager) will be prioritized if possible.

If the controls indicate the high error rate, or it will be necessary to solve the problem at the study site, the issue will be escalated to the sponsor and local CRO. The Local CRO will arrange a visit to the site to solve the issue on-site (on-site data monitoring to verify the process and data).

Risk assessment (chapter 6) is applied throughout the Study lifecycle and involved in all its parts from the Study design through preparation (protocol development, ...) and execution to the final evaluation.

Based on Risk assessment results, the following monitoring methods are applicable throughout the whole Study: centralized statistical monitoring and on-site-monitoring. Details are described in the Monitoring Plan.

CONFIDENTIAL

Confidential	MyRisk	Date: 05 February 2024
	Protocol	
	PROTOCOL NUMBER: IBA1160	Version: 5.1

[figure not shown]
## 6. Risk Management and Risk Assessment

Risk management will be applied on all processes (contracts management, recruitment management, training of investigators, data collection and data processing, data review, data analyses, etc.) throughout all trial lifecycle to ensure human subject protection and the reliability of the trial results in compliance with requirements of ICH E6 Guideline for Good Clinical Practice.

The trial will be based on a Risk-based approach, it means that:

- All critical processes, that are essential for human subject protection and reliability of results will be identified (methods of operation and setting of the study, crucial processes such as ICF collecting, regulatory processes, SOPs/manuals, and their training, budget risks, etc).
- Risks will be evaluated on the base of a probability of occurring, their detectability and severity, and considered with the predefined quality tolerance limits.
- If nonacceptable risk will be defined, the corrective or/and preventive actions will be implemented to reduce the risk to an acceptable level. Detected risks, CAPA, responsibilities, and the schedule of risk monitoring will be summarized in the document Risk assessment report.
- The risks will be communicated with interested participated subjects (sponsor, cooperating CROs, investigators) adequately.
- The risks will be reviewed periodically according to the Risk management Plan, which is a part of the Risk assessment report and Quality Control Plan, that will be prepared as separate documents on the base of Risk analyses.

The Risk management is illustrated on the following figure:

**Figure 1** The scheme of Risk management in the trial

CONFIDENTIAL

Confidential	MyRisk	Date: 05 February 2024
	Protocol	
	PROTOCOL NUMBER: IBA1160	Version: 5.1

For risk analyses, a methodology FMEA (Failure Mode and Effects Evaluation) will be used. It is a risk management tool to proactively identify and assess the causes and effects of potential failures in a system, thereby preventing them from happening. All considered risks are assessed according to Risk priority number (RPN) considering severity (how severe is the consequence if the process fails), occurrence or probability (how often or how is probable, that process fails), detection (how easily can failure be detected). This Risk analysis will be processed as a separate document according to IBA's Working instruction. FMEA is a multidisciplinary method, so the sponsor and IBA experts will participate in its processing, evaluation, and implementation of preventive actions.

## 7. Data Collection and Data Management

IBA will manage all data management activities for the study.

Data will be collected into the database behind the EDC system **CLADE-IS** (see Appendix 6). The system has been specifically designed for the collection of large amounts of data in clinical trials and/or clinical registries. It will be fully customized to the structure and requirements of the project. The online application is accessible to users via any internet browser. Records are stored under a specific identity number (ID) which does not allow any backward identification of any individual patient. The unequivocal identification of the patient is only known to the treating physician or authorized healthcare professional.

Clinical management of the patient reflects the standard clinical practice in each country/center. Data (no patient's initials, no full date of birth will be collected) from all patients who meet inclusion criteria will be consecutively entered in the project database.

Each patient will fill the Patient's diary for 5 consecutive days after each chemotherapy administration, MAT questionnaire during the first 24 hours following chemotherapy, and four days after chemotherapy, and FLIE quality of life (QoL) questionnaire on 6th day after each chemotherapy. FLIE QoL questionnaire and MAT questionnaire will be available in validated translation for each country. Patient diaries will be available in local languages for each country. Patients included in the study shall undergo 3 consecutive chemotherapy cycles. Data from the Patient's diary and MAT will be digitalized onsite to become part of the electronic database. IBA will do the quality control process of digitalized patient diaries and MAT data. FLIE QoL questionnaires will be periodically sent to IBA for digitalization and following quality control.

Specific data management documentation will be prepared by IBA. Firstly, it will be the Data Management Plan containing detailed information about database setup (form statuses, user roles, type of validations, reporting, and database specialties) and detailed information about consequential data management processes and relevant documents (Quality Control Plan, Translation, and Coding or SAE Reconciliation Plan). Secondly, it will be the Data Validation Plan containing the plan of all checks planned to be performed on collected data. All particular documents will be prepared by IBA and approved separately. Data management plan and Data validation plan will be issued prior to data collection beginning. Data will be collected in eCRF by the Investigator(s) or trained study member. Every person authorised to enter project data into eCRF will receive a login and password granted exclusive access to him/her. Data will be entered into the system according to the technical manual that will be provided to all users by IBA in the same languages as eCRF (English and local languages where required (e.g., Chinese, German)).

Control of data correctness will be performed in several steps.

- 1) Automatic validations: The first and most extensive step is automatic control performed according to pre-programmed checks based on Data Validation Plan. The system will generate queries based

CONFIDENTIAL

Confidential	MyRisk	Date: 05 February 2024
	Protocol	
	PROTOCOL NUMBER: IBA1160	Version: 5.1

on these checks and investigators will have to answer them. Most of system queries could be generated in local languages.

- 2) Manual queries: The second step is the possibility to create manual queries based on specific findings realised by any member of the project team (especially after the data review process). These queries will be created in English and answers will be requested in English too.
- 3) Data review: Data review process will be organised regularly (quarterly) and will be one of the key project milestones focusing on the quality of collected data and accuracy of data collection and data cleaning process (details of the data review process in the paragraph below).
- 4) Quality Control of Patient's diaries and MAT data. Patient's diaries and MAT data will be digitalized on clinical sites. The patient's diaries and MAT questionnaires will be sent to IBA then and submitted to the quality control process (details of the quality control process in the paragraph below).
- 5) Quality Control of FLIE data. FLIE data will be sent to IBA and then digitalized. The quality control process will be applied to them too.

### Data Review Process

The goal of the data review process is to review collected data during the course of the project in order to verify data quality, confirm the accuracy of data collection and data cleaning processes, and eventually to update the established process. The data review process will be organised regularly. At each time data review will be performed, an agenda containing a list of actions will be prepared. The following items will be considered for review:

- A global overview of subjects and their database statuses. This overview will present detailed enrolment and how rigorously investigators are working with the EDC system. The data manager will prepare this overview.
- Medical review of specific predefined consistencies of medical information. The Scientific Lead will be in charge to review key medical data in order to provide information on whether collected data are all right from the medical perspective (review of used medication, adverse events, etc.). The Scientific Lead will work with data provided by the data manager in advance to the data review meeting.
- The total number of outstanding queries in particular sites compared to the global number of open queries. The number of totals/open queries can show how rigorously investigators are working with the EDC system and their will to correct found inconsistencies. The list of queries will be prepared by the data manager.
- List of specific data inconsistencies. In addition to system queries raised during the data collection process, there might be inconsistencies found during medical coding, SAE reconciliation, or analytical data review. These issues will be prepared by the project manager and will be discussed too.
- Plan of remaining steps until the nearest milestone. A review of the study calendar will be part of each data review meeting. Following on enrolment status, plan of enrolment for the next study period will be discussed as well as the number of participating countries, planned FPI/LPO milestones, the status of patient diaries tracking, etc. This item will be prepared by the project manager.
- Overview and classification of protocol deviations as defined by the Sponsor and the Scientific Lead. Based on already collected data there might be information about existing protocol deviations. The data analyst will prepare a list of all known protocol deviations in order to discuss all relevant patients. The following deviations will be considered:
  - fulfillment of inclusion criteria
  - violation of exclusion criteria
  - study visits not corresponding to the study design

CONFIDENTIAL

Confidential	MyRisk	Date: 05 February 2024
	Protocol	
	PROTOCOL NUMBER: IBA1160	Version: 5.1

Data Review Process will be built on the agenda prepared by the project manager according to the above-mentioned points and containing all details to be discussed during the meeting. It is important to invite all relevant people in order to arrange a constructive discussion leading to appropriate conclusions, at least Helsinn representative, Scientific Lead, and IBA project manager will participate. All the decisions made during the meeting will be written, reviewed by all participants, and approved. Meeting minutes will include all the tasks resulting from the meeting and solutions of discovered issues.

### **Quality Control Process**

The principle of the quality control process is to compare original data with data transferred into the clinical database. This process will be applied on FLIE QoL questionnaires (as these are only data being entered into the clinical database out of clinical site) and Patient's diaries and MAT questionnaires (as these data will be digitalized as well). Initially, a Quality Control Plan will be created to plan the frequency of quality control process, list of items to be checked, permitted error rate, and other processing details. The results of the quality control process will be presented in the Quality Control report.

## **7.1. Data Quality Control**

The purpose of data control in the clinical trial is to verify that:

- The rights and well-being of human subjects are protected
- The reported data are accurate, complete, and verifiable with source documents
- The conduct of the trial is in accordance with the current protocol, GCP, and regulatory requirement

Within this trial, the risk-based approach to data quality control of clinical trial will be implemented. There will be no on-site monitoring involved from the IBA side. Data verification will be set by using the EDC system. There will be no monitoring of source documentation. The potential risks of this approach will be considered within the Risk assessment and the necessary measures will be implemented. The key points in this approach are:

- The standard operating procedures
- Contracts with the sites/investigators
- Qualification and training of participating subjects (investigators/local CROs/IBA....)
- eCRF and validation of the EDC system
- Risk management and communication of risks
- Data review (the quality of processed data will be verified by a process of Data review)
- Quality Control is performed on digitalized data (will be described in the Quality Control Plan).

### **Data review**

The purpose of regular data reviews as well as single use before analysis is:

- a) Identify missing data, inconsistent data, data outliers, unexpected lack of variability, and protocol deviation
- b) Examine data trends such as the range, consistency, and variability of data within and across sites.
- c) Evaluate for systematic or significant errors in data collection and reporting at a site or across sites; or potential data manipulation or data integrity problems.
- d) Analyse site characteristics and performance metrics.
- e) Select sites and/or processes for targeted on-site monitoring.

CONFIDENTIAL

Confidential	MyRisk	Date: 05 February 2024
	Protocol	
	PROTOCOL NUMBER: IBA1160	Version: 5.1

## 8. Statistical analysis

The data will be statistically processed, analyzed, and evaluated centrally by the Institute of Biostatistics and Analyses, Ltd., [name].

### 8.1. Statistical Analysis Plan

Detailed data processing procedure will be described in the Statistical Analysis Plan (SAP) with regard to the nature of the primary and secondary endpoints of the study and all the other data collected via the Electronic Data Collection (EDC) system. The SAP will be implemented as soon as the protocol will be finalized.

### 8.2. Sample Size Analysis

A sample of 410 randomised subjects, each scheduled to be measured 3 times/cycles, achieve a 80% power when using a two-sided Wald test from a GEE analysis to test whether the proportion of Complete response expected in the Test group (71%) differs from that expected in the Control group (60%) at a significance level of 0,050. The subjects are randomly split between a Test group and a Control group, with 50% of the subjects assigned to the Test group. The measurements of each subject will be made at the following times/cycles expressed as proportions of the total study time: {0%; 50%; 100%}. Missing values are assumed to occur completely at random (MCAR) or at random (MAR). These missing value proportions will be combined to form the pairwise observant probabilities using the Independent method. The anticipated proportions missing at each measurement time/cycle are {0%; 7.5%; 15%}. Based on these attrition rate scenario, a sample of 348 completer subjects is expected. The correlation between observations on the same subject is assumed to be 0.5 (ballpark estimate). All computations are performed using PASS 14 software.

### 8.3. Analysis Populations Sets

The Full Analysis Set (FAS) will consist of all randomized patients to whom the investigational drug is dispensed. It will be the primary basis for the analyses of efficacy. Following the intent-to-treat principle, patients in the FAS population will be analyzed according to the treatment to which they were randomized. A Per Protocol (PP) population will consist of all patients in the FAS population who complete the study fully compliant with the protocol and without any major deviation. Patients in the PP population will be analyzed according to the treatment they received. Efficacy analyses based on the PP population will be considered supportive.

The Safety population is defined as the set of all randomized patients with at least one documented application of any study drug. It will be the basis for the analyses of safety. Patients in the Safety population will be analyzed according to the treatment they received.

### 8.4. Efficacy Analysis

All efficacy analyses will be performed on the FAS population. Also, analysis of the primary and secondary efficacy variables will be carried out on the Per Protocol population to assess the robustness of the findings. Safety outcomes will be analyzed on the Safety population.

CONFIDENTIAL

Confidential	MyRisk	Date: 05 February 2024
	Protocol	
	PROTOCOL NUMBER: IBA1160	Version: 5.1

The primary efficacy endpoint “Proportion of complete responses over three cycles of chemotherapy after the start of the MEC administration” will be analyzed by means of a generalized linear model (GLIM) with logit link function, binomial distribution, and with “study treatment” (NEPA + Dex or Standard of care), “carboplatin use” (yes or no) and “country” as factors. Moreover, the GLIM model will be parameterized with generalized estimating equations with an exchangeable working correlation matrix to take into account clustered data (i.e. three repeated measures corresponding to as many cycles of chemotherapy within each subject). Results will be reported as odds ratios with associated two-sided 95% confidence intervals and p-values.

The same statistical approach will be used for all the secondary efficacy endpoints except for the following outcomes “delay and/or dose reduction” which will be analyzed using a Stratified Wilcoxon Rank Sum test blocking for carboplatin use and country.

Missing data on the primary efficacy endpoint will be imputed using conventional Multiple Imputations approach. The SAS® MI procedure will be employed to perform multiple imputation in order to obtain Maximum Likelihood estimates which, by definition, are unbiased under a MCAR and MAR mechanism for missing values. Details on Multiple Imputations will be provided with the SAP.

Missing data on secondary efficacy endpoints will be imputed using last observation carried forward (LOCF). The overall type I family-wise error rate for testing the primary and the secondary efficacy parameters is controlled at the 0.05 significance level without the need for adjustments since the study is planned with a single primary endpoint and since secondary endpoints are only supportive of primary endpoint findings. All statistical analyses will be performed using SAS version 9.4 or later.

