## Study rationale and background

Despite the availability of effective antiemetics and evidence-based guidelines, up to 40% of cancer patients receiving chemotherapy fail to achieve complete nausea and vomiting control.

Antiemetic guidelines recommendations are based on the emetogenic potential of the chemotherapy. Chemotherapy (CT) agents are divided in Highly, Moderately, Low and Minimally Emetogenic potential (HEC, MEC, LEC, MiE).

In addition to type of chemotherapy, several patient-related risk factors can increase the risk of CINV. Currently, there is limited consensus surrounding the most relevant patient risk factors that may predict the risk of CINV. Based on a recent study by Dranitsaris et al. (Dranitsaris et al. Ann Oncol. 2017 Jun 1; 28(6):1260-1267.), eight (8) predictive factors have been identified and an algorithm has been developed to incorporate these factors into the optimal selection of prophylactic antiemetics:

1. nausea and/or vomiting in the prior cycle of chemotherapy
2. use of non-prescribed antiemetics at home in the prior cycle of chemotherapy
3. platinum or anthracycline-based chemotherapy
4. age < 60 years
5. expectations for (anticipating) nausea and/or vomiting
6. <7 h of sleep the night before chemotherapy
7. history of morning sickness during previous pregnancy
8. cycle of chemotherapy (A negative association between risk and number of cycles was identified where the hazard for CINV was highest in cycles 1 and 2, with a gradual decline and plateau from cycle 3 onward).

The clinical application of this prediction tool has the potential to be an important resource for clinicians and may help to enhance patient care by optimizing the use of the antiemetics in a proactive manner.

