### 3.6.3. Study visits procedure

No study-specific activities will be completed before signed informed consent form is obtained from patients. Study procedure covers five patient's visits at the site.

#### Visit 0

Visit 0 is a screening visit conducted within 2 weeks before chemotherapy administration on cycle 1 or alternatively on Day 1 of chemotherapy Cycle 1. The case of Visit 0 and 1 are combined the patient will still be given adequate time for consideration and consent before the study enrolment.

Investigator considers whether the selected patient meets the predefined eligibility criteria. All predictive individual factors as reported earlier will be collected in eCRF. The risk score will be calculated automatically based on predictive factors No. 1 – 7 (see 3.3.3. Risk Factors for CINV). These parameters will be used to identify the patients with a CINV risk score  $\geq 13$  (see 3.3.1. Inclusion Criteria). If the patient complies with all the inclusion and exclusion criteria and signs informed consent, he/she is enrolled in the study. If the patient is WOCBP a pregnancy test is done to confirm eligibility. Data from screening visit will be collected in appropriate forms in eCRF.

The randomization procedure can be conducted either during Visit 0, Visit 1 or any time between Visit 0 and Visit 1. The patient is randomized by using an algorithm in eCRF into one of the intervention groups (see sections 3.4. Intervention and antiemetic treatment and 3.4.2. Randomization procedure). If randomization occurs any time before visit 1, it is required to check during Visit 1 that the patient receives the correct treatment assigned according to the intervention groups. The drugs must be correctly stored between the randomization and drug administration at Visit 1.

#### Visit 1

Visit 1 is a visit on Day 1 of chemotherapy Cycle 1.

WOCBP are tested for pregnancy by a urine dipstick prior to dosing the antiemetic treatment.

The patient is asked about the additional predictive factors (anxiety in the previous 24 hours &  $<7$ h of sleep the night before chemotherapy).

The patient is assigned to the treatment and randomized by using an algorithm in eCRF into one of the intervention groups (see sections 3.4. Intervention and antiemetic treatment and 3.4.2. Randomization procedure).

The patient receives antiemetic and chemotherapy at a due time after antiemetic is given.

Data of cycle 1 is collected in eCRF in an appropriate form.

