9.4.1. Imputation of endpoints data

To achieve the largest possible sample, imputation techniques will be used to impute missing data for the FAS population. Missing data on the primary efficacy endpoint will be imputed using conventional Multiple Imputations approach. The SAS® MI procedure will be employed to perform multiple imputation in order to obtain Maximum Likelihood estimates which, by definition, are unbiased under a MCAR and MAR mechanism for missing values.

The following MI procedure code will be used to perform MI with 5 imputations.

```
PROC MI data = dataset seed=s out = MIdataset n impute = 5;
VAR study_treatment carboplatin country vis1_event - vis3_event;
CLASS study_treatment carboplatin country vis1_event - vis3_event;
monotone logistic;
RUN;
```

The exact names of the variables may differ.

9.4.2. Missing data within the FAS population on secondary efficacy endpoints will be imputed using the last observation carried forward (LOCF). Primary Efficacy Endpoint

The primary efficacy endpoint “Proportion of complete responses over three cycles of chemotherapy after the start of the MEC administration” will be analyzed by means of a generalized linear model (GLIM) with logit link function, binomial distribution and with “study treatment” (NEPA + Dex or Standard of care), “carboplatin use” (yes or no) and “country” as factors, using data from the overall period of three cycles.

Moreover, the GLIM model will be parameterized with generalized estimating equations with an exchangeable working correlation matrix to take into account clustered data (i.e. three repeated measures corresponding to as many cycles of chemotherapy within each subject). Results will be reported as odds ratios with associated two-sided 95% confidence intervals and p-values.

The results will be obtained via the GENMOD procedure, using following code:

```
PROC GENMOD data = dataset;
CLASS id study_treatment carboplatin country;
MODEL complete_response = study_treatment carboplatin country / dist = bin
link = logit;
REPEATED subject = id / type = exch covb corrw;
LSMEANS study_treatment / diff exp ilink cl;
RUN;
```

The exact names of the variables may differ.

With MI the code will be modified to:

```
PROC GENMOD data = dataset;
CLASS id study_treatment carboplatin country;
MODEL complete_response = study_treatment carboplatin country / dist = bin
link = logit;
REPEATED subject = id / type = exch ecovb;
LSMEANS study_treatment / diff exp ilink cl;

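### The primary GEE model omits the Visit 0 CINV risk score; pre-specifying it as a covariate would gain a little power without extra patients or data

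*Protocol*

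**What the plan says.** Protocol 8.4 specifies a logit model fitted by GEE with an exchangeable working correlation, with study treatment, "carboplatin use” (yes or no) and “country” as factors". The GENMOD code in SAP 9.4.2 matches it: "MODEL complete_response = study_treatment carboplatin country / dist = bin". The second GENMOD block, for the imputed data, has the same terms. The PROC MI VAR statement in SAP 9.4.1 lists treatment, carboplatin, country and the three cycle outcomes.

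The two covariates are the two stratification factors (Protocol 3.4.2; SAP 5.2).

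At Visit 0, Protocol 3.6.3 states: "All predictive individual factors as reported earlier will be collected in eCRF". The eCRF computes the score from factors 1 to 7, and only patients scoring 13 or more are randomised (Protocol 3.3.1, 3.3.3, 3.6.3.2). The score is recalculated at Visits 2 and 3 without effect on participation or arm. SAP Table 14.1-8 tabulates the screening risk parameters, and SAP 9.8 examines the risk factors in a separate analysis.

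**The concern.** The trial rests on the premise that this score predicts CINV. It is known before randomisation for every patient, yet neither the randomisation nor the primary model uses it beyond the entry threshold.

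Two things are at stake. If the score is prognostic among eligible patients, leaving it out gives up some power. And if the arms differ on it by chance, nothing in the primary analysis corrects for that. Table 14.1-8 would show such an imbalance, but an adjustment chosen after seeing it would not be credible. The choice has to be made in advance.

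**Working it through.** **1. The plan's own figure.** Protocol 8.2 says 410 patients "achieve a 80% power" with a "two-sided Wald test from a GEE analysis", two-sided alpha 0.05, 71% v 60%, 1:1 allocation, three cycles, missing proportions 0, 7.5 and 15% combined by the independent method, and correlation 0.5.

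Observed proportions are 1, 0.925 and 0.85. Their sum is 2.775, and the sum of pairwise products is 0.925 + 0.85 + 0.786 = 2.561.

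k = (2.775 + 2 × 0.5 × 2.561) / 2.775² = 0.693

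N = (1.960 + 0.842)² × k × [1/(0.5 × 0.71 × 0.29) + 1/(0.5 × 0.60 × 0.40)] / (logit 0.71 − logit 0.60)²

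= 7.849 × 0.693 × 18.05 / 0.2400 ≈ 409

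Power at 410 is 80.1%. The stated figure reproduces, with no covariate gain assumed.

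**2. How far the score can vary.** From the table in Protocol 3.6.3.1:
- Scored as first cycle: 10 plus at most 1 + 1 + 1 + 2, so eligible scores are 13, 14 or 15. Without platinum or anthracycline only 13 is possible.
- Scored as second cycle: up to 18, if every factor is present.
- Scored as third cycle or later: up to 17.

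The documents do not give the mix of entry cycles.

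**3. Gain from adding the score.** Its strength among patients scoring 13 or more is not in the documents. The assumed range is an odds ratio for failure of 1.0 to 2.0 per point, with scores 13/14/15 in 45/40/15% of patients. Two simulation sets used 410 patients, 71% v 60%, the stated missingness, an exchangeable GEE and robust SEs. Set A had 2,500 runs per scenario and within-patient correlation 0.5. Set B had 6,000 runs and correlation about 0.46 to 0.49. Each cell shows the value without, then with, the score.

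| Odds ratio per point | Power %, set A | SE of log OR, set A | SD of standardised log OR, set A | Power %, set B | Relative efficiency, risk difference, set B |
|---|---|---|---|---|---|
| 1.0 | 81.0, 81.0 | 0.1717, 0.1720 | 0.1736, 0.1739 | 81.2, 81.3 | 1.00 |
| 1.25 | 80.8, 81.2 | 0.1725, 0.1731 | 0.1728, 0.1723 | 82.2, 82.2 | 1.01 |
| 1.5 | 81.7, 82.6 | 0.1724, 0.1736 | 0.1724, 0.1702 | 82.2, 83.4 | 1.03 |
| 2.0 | 81.6, 85.5 | 0.1724, 0.1753 | 0.1708, 0.1642 | 80.5, 83.9 | 1.08 |

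Monte Carlo error is about 0.8 points (set A) or 0.5 points (set B) per power figure; the paired differences are more precise. In set B the mean risk difference stayed at about 0.110. Its SD fell from 0.0389 to 0.0374 at odds ratio 2.0, and (0.0389/0.0374)² = 1.08, equivalent to about 0.08 × 410 ≈ 33 patients.

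With a wider assumed spread (13 to 18; 1,500 runs; score and cycle added together; odds ratios 1.25, 1.5 and 1.75), power went from 80.1 to 80.3, 81.7 to 83.9 and 81.1 to 84.4%.

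**4. Which scale improves.** The SE of the log odds ratio does not fall in any row. At odds ratio 2.0 the estimate moves from 0.489 to 0.520, because the target changes from a marginal to a score-conditional odds ratio. The ratio to its SE rises from 0.489/0.1724 = 2.84 to 0.520/0.1753 = 2.97, which is where the power comes from. When both models are put on the same marginal target (standardised log odds ratio or risk difference), precision improves.

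**The case against.** The strongest reply is that nothing here is broken. The model adjusts for exactly the stratification factors, 410 reproduces without covariate gain, the risk parameters are tabulated, and the risk factors have their own analysis. All of that stands, and it limits the point to an optional improvement.

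The size is also open to challenge. Eligibility removes much of the score's variation. An odds ratio of 2.0 per point means fourfold odds of failure between scores 13 and 15, within a group already selected as high risk, so the top row is generous. Set A left carboplatin and country out of every model. Carboplatin already carries part of the platinum item, so the gain over the plan's actual model may be smaller. These points also stand.

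A reader might infer more than the documents support:
- **That a cycle term would add precision.** The protocol says "the hazard for CINV was highest in cycles 1 and 2, with a gradual decline and plateau from cycle 3 onward", but adding study cycle alone changed power by −0.1 to +0.7 points, since cycle is nearly balanced across arms. That statement also concerns chemotherapy cycle number, which can differ from study cycle in non-naive patients.
- **That cycle is missing from the imputation.** PROC MI is in wide format, with a separate model for each cycle's outcome given the earlier ones, so cycle is built in. Only the baseline score is absent, and no calculation here shows that this undermines the missing-at-random assumption.
- **That prior-cycle nausea or vomiting is a strong predictor for everyone.** It does not apply to chemotherapy-naive patients, and it is set to no for patients restarting after six months or more. Entry at the third cycle or later requires it, and every eligible second-cycle combination but one includes it. Given entry cycle it is nearly constant.

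**Conclusion.** The primary analysis leaves out a pre-randomisation value that the trial already holds and regards as predictive. Pre-specifying the Visit 0 score would be an improvement with a small gain: about 0 to 4 points of power for assumed odds ratios of 1.25 to 2.0 per point, and no measurable loss if the score is not prognostic. It would also deal with chance imbalance in the score.

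The range depends on the assumed prognostic strength and score distribution, neither of which the documents give. The 97.4% sensitivity in Protocol 3.6.1 describes the cut-off, not how failure varies above it.

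Two further inferences should be resisted. The stated 80% power at 410 is not wrong, so the omission does not leave the trial underpowered on its own assumptions. And a tighter odds-ratio interval should not be expected; the benefit shows in the test and on the risk-difference scale.

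**What to change.** Before database lock, and preferably before any by-arm country summary under SAP 9.9:

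- Name the Visit 0 risk score, as a single linear term, as a covariate in Protocol 8.4.
- Add it to both GENMOD MODEL statements, to the PROC MI VAR statement ahead of vis1_event, and to MODELEFFECTS in MIANALYZE.
- State that the scores recalculated at cycles 2 and 3 will not be used. They contain prior-cycle outcomes that treatment can affect.
- State that the odds ratio is conditional on the score. Beside it, report standardised complete response proportions by arm and their difference, pooled over the imputations, so that the result can be read against the planned 71% v 60%.

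This needs no extra patients, visits or data. It is more than a line of code: SAP section 2 declares no changes from the protocol, so both documents must be amended together, and the standardised proportions need code and a stated variance method. If the sponsor prefers to keep the marginal odds ratio as primary, the score-adjusted model can be pre-specified as a sensitivity analysis. That gives up the power gain in the primary test but keeps a planned answer to any imbalance.
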